8.3.2.1. Safety MRI

The number and percentage of subjects with presence of screening safety MRI abnormalities along with the type of abnormality and primary location of abnormality reported will be presented by treatment group. Additionally, abnormality sequence, abnormality status, and presence of white matter disease will be tabulated by treatment group. The number and percentage of subjects whose screening safety MRI findings suggest there is a potential alternative diagnosis to PD will also be presented.

Screening safety MRI results will be listed.

8.3.2.2. Volumetric MRI

Volume will be summarized using descriptive statistics for the left, right, and bilateral sides of the following locations:

- Whole brain (bilateral only)
- Lateral ventricles (bilateral only)
- Intracranial (bilateral only)
- Cortical
- Hippocampus
-

Cerebral cortex average thickness will be summarized using descriptive statistics for the left, right, and bilateral sides of the following locations:

- Cortical

Statistical Analysis Plan,
Sponsor Alkahest, Inc.
Protocol Number ALK6021-201
PCN Number ALKA7951

- Mayo (bilateral only)
- Prefrontal lobe
- Whole temporal lobe
- Superior temporal lobe
- Medial temporal lobe
- Lateral parietal lobe
- Inferior parietal lobe
- Precuneus
- Isthmus-cingulate
- Entorhinal cortex

Atrophy absolute change and cerebral cortex thickness average change will be summarized using descriptive statistics for the left, right, and bilateral sides of the following locations at follow-up:

- Whole brain (bilateral only)
- Lateral ventricles (bilateral only)
- Cortical
- Hippocampus

Additionally, cerebral cortex thickness average change will be summarized using descriptive statistics for the left, right, and bilateral sides of the following locations at follow-up:

- Cortical
- Hippocampus
- Mayo (bilateral only)
- Prefrontal lobe
- Whole temporal lobe
- Superior temporal lobe
- Medial temporal lobe
- Lateral parietal lobe
- Inferior parietal lobe
- Precuneus
- Isthmus-cingulate
- Entorhinal cortex

Volumetric MRI results will also be listed.

8.3.2.3. Resting fMRI

Since there are 85 correlations between regions, fMRI data will not be summarized or listed due to file size. If summaries or listings are desired, they will be provided on an ad hoc basis.

8.3.2.4. ASL MRI

Cerebral blood flow measurements will be summarized using descriptive statistics for the left, right, and bilateral sides of the following locations:

- Frontal lobe

Statistical Analysis Plan,
Sponsor Alkahest, Inc.
Protocol Number ALK6021-201
PCN Number ALKA7951

- Cingulate cortex
- Parietal lobe
- Temporal lobe
- Occipital lobe
- Striatum
- Cerebellum
- Thalamus
- Pallidum
- Substantia nigra
- Hippocampus

ASL MRI results will also be listed.

9. Safety and Tolerability Analysis

The primary endpoint of this study is the incidence of TEAEs and SAEs identified by MedDRA PT and grouped by MedDRA SOC.

The secondary safety endpoints are as follows:

- Change from baseline in clinical laboratory parameters
- Change from baseline in vital sign measurements
- Change from baseline in body weight
- Change from baseline in the S-STs

Safety will also be evaluated from electrocardiogram (ECG) results and physical examination results.

All safety analyses will be performed on the Safety Set.

9.1. Adverse Events

All AEs that occur after the time of treatment with the study agent will be considered TEAEs. Events meeting this definition will be those events that are a change from the subject's baseline conditions, including an increase in frequency or severity (these will be entered as new AEs). For AEs occurring on the date of first dose, if the time of onset is missing, the AE will be assumed to be treatment emergent.

All AEs, TEAEs, and SAEs will be coded using the MedDRA Version 20.1 or higher coding dictionary. The AE analyses will focus on those that are treatment emergent, however any AEs that are reported after consent has been signed and before initial dosing will be considered intercurrent events and flagged in the listings as such.

The causal relationship of the AE to the study drug is determined by the investigator as Unrelated, Possibly Related, or Definitely Related. These can be mapped to Unrelated (*Unrelated*) and Related (*Possibly Related* and *Definitely Related*). Adverse event summaries will be repeated for treatment related TEAEs.

Adverse events severity grades are reported as mild, moderate, or severe.

Summaries of incidence rates (frequencies and percentages) of individual TEAEs will be presented by SOC, PT, and treatment group. Such summaries will be displayed for all TEAEs, TEAEs by maximum severity, and TEAEs by relationship.

Each subject will be counted only once within each summation level (SOC and PT). If a subject experiences more than 1 TEAE within each summation level only, the TEAE with the strongest relationship or the maximum severity, as appropriate, will be included in the summaries of relationship and severity. If a particular event is missing the severity and/or relationship, then the strongest possible severity or relationship will be assumed for analysis (severity = severe, relationship = definitely related).

Incidences will be presented by descending frequency of SOC and PT within SOC, and then alphabetically within PT where the incidence is the same; this is based on overall subjects then alphabetically in case of a tie.

Missing and partially missing AE start and/or stop dates will be imputed, for the purpose of statistical analysis, according to the specifications described in Section 6.1.8.

In the AE data listings, all AEs will be displayed. AEs that are treatment emergent will be flagged.

A test of hypothesis comparing the proportion of subjects reporting a TEAE throughout the study will be conducted using a Chi-square test or Fisher's exact test, as appropriate. The null hypothesis is that there is no difference in proportion between treatment groups, with a two-sided alternative that considers the possibility of a difference in either direction. The number and percentage of subjects reporting a TEAE and the 95% Wilson confidence interval (CI) for the proportion will be presented for each treatment group. In addition, the difference in proportions between the GRF6021 and placebo groups and the 95% Wilson CI will be presented. The same statistics and hypothesis testing will be performed for subjects reporting an SAE throughout the study.

9.1.1. Adverse Events Leading to Withdrawal

A derived action taken variable will be created for subjects who withdrew from the study or study drug due to an AE as noted on the study completion (DS) CRF. If the reason for discontinuation entered on the DS CRF was "Adverse Event" and the AE occurred between the start of the first infusion in Period 1 through the final infusion in Period 2, the derived action taken will be set to "study drug withdrawn" regardless of what action taken was entered on the AE CRF. Since treatment is administered during two distinct periods and not on a continuous basis, if an AE that causes withdrawal occurs between the two infusion periods, action taken may not accurately indicate "study drug withdrawn" unless it was decided that subject would not get a second infusion since the subject will not actively be receiving treatment between the two periods.

A summary of incidence rates (frequencies and percentages) of TEAEs leading to withdrawal of study drug, by treatment group, SOC, and PT will be prepared for the Safety Dataset. No inferential statistical tests will be performed. These summaries will be based on the derived action taken.

A data listing of AEs leading to withdrawal of study drug will be provided, displaying details of the event(s) captured on the CRF. Both derived and CRF action taken variables will be presented in the listing.

9.1.2. Deaths and Serious Adverse Events

Any deaths that occur during the study will be listed.

Serious adverse events will be listed and tabulated by SOC, PT, and treatment group.

9.1.3. Other Significant Adverse Events

AEs of special interest (AESI) are defined in the protocol. These are to be considered as Adverse Events by the PI in order to be recorded:

A summary tabulating these criteria for safety will be presented by SOC, PT, and treatment group. All AESIs will be flagged in the AE listings.

Adverse events with preferred terms associated with blood pressure changes will also be presented by infusion period, SOC, PT, and treatment group. Infusion period will be further categorized by whether the event start date occurred during the infusion period or after the infusion period. Examples of such events can be identified by the following preferred terms: blood pressure decreased, blood pressure diastolic decreased, blood pressure systolic decreased, blood pressure increased, increased blood pressure, blood pressure diastolic increased, blood pressure systolic increased, hypotension, hypertension, low blood pressure, high blood pressure. This is a non-exhaustive list and a review of AE MedDRA coding will be conducted prior to lock to identify all events associated with blood pressure changes.

9.2. Laboratory Evaluations

The screening safety lab panel includes: all comprehensive labs (hematology, chemistry, coagulation, urinalysis, urine chemistry, ionized calcium), immunochemistry (HIV, hepatitis B, hepatitis C, thyroid-stimulating hormone (TSH), brain natriuretic peptide (BNP)), cobalamin (vitamin B12), pyridoxine (vitamin B6), thiamine (vitamin B1), direct antiglobulin test, IgA, haptoglobin, and C1 inhibitor. The urine drug screen includes cannabinoids, benzodiazepine, barbiturates, opiates, cocaine, amphetamines, methadone, phencyclidine, and propoxyphene.

Pre-infusion safety labs will be performed onsite and should be collected and results interpreted prior to the following day's infusion start. The following should be measured at Visit 3, Visit 4, Visit 6, Visit 11, Visit 12, and Visit 14: sodium (Na), potassium (K), ionized calcium, urea nitrogen (BUN)/urea, creatinine (Crea), hematocrit, hemoglobin, platelets. These results are only available at each site and will therefore not be summarized.

The exit safety lab panel includes all comprehensive labs, immunochemistry, direct antiglobulin test, and ionized calcium.

Comprehensive labs will be performed at screening/Visit 1, Visit 6, Visit 8, Visit 9, Visit 14, Visit 16, Visit 17, and upon exit/Visit 19.

Laboratory test results, excluding the site's pre-infusion safety labs mentioned above, will be summarized descriptively by treatment and visit as both observed values and change from baseline values for each parameter. Categorical urinalysis results will be summarized using frequencies by treatment group and visit.

Shifts from baseline for clinical laboratory values below, within, or above the normal range will be provided for hematology, chemistry, coagulation, and quantitative urinalysis results by visit and treatment. See Section 6.1.1 for the definition of baseline.

Subjects with significant laboratory abnormalities will be identified in data listings. If any laboratory tests are collected at an unscheduled visit post-baseline, the results will be included in listings.

Pregnancy test results from Screening (Visit 1), Visit 3, and Visit 11 will be listed.

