5 STUDY ENROLLMENT AND WITHDRAWAL

5.1 INCLUSION CRITERIA

In order to be eligible for inclusion, all subjects must meet the following criteria:

1. Aged 40-85 years at time of enrollment, inclusive.
2. Diagnosis of clinically established or clinically probable PD according to MDS-PD criteria (Postuma 2015)(Appendix 8) with at least 1 year of PD symptoms.
3. Diagnosis of PD-MCI (Level I, i.e. impairment on a scale of global cognitive abilities validated for

- use in PD) or probable or possible PDD according to MDS criteria (Litvan 2012, Emre 2007)(Appendix 9).
4. Score on the MoCA of 13-25, inclusive (Nasreddine 2005)(Appendix 1).
 5. Hoehn and Yahr Stages 1-4.
 6. If on dopaminergic therapy (e.g., levodopa, dopamine agonists, monoamine oxidase inhibitors, catechol-O-methyl transferase inhibitors, amantadine), must be on stable dosage at least 4 weeks prior to baseline.
 7. If on medications for cognition (e.g., rivastigmine, galantamine, donepezil, memantine), must be on stable dosage for at least 8 weeks prior to baseline.
 8. If on antidepressant medications, must be on stable dosage for at least 8 weeks prior to baseline.
 9. If on clozapine, quetiapine, or pimavanserin, must be on stable dosage for 8 weeks prior to baseline.
 10. Renal function as defined by estimated glomerular filtration rate (eGFR) ≥ 45 mL/min/1.73 m² using the Modification of Diet in Renal Disease (MDRD) study equation and no microalbuminuria.
 11. Systolic ejection fraction of $\geq 55\%$ on trans-thoracic echocardiogram.
 12. Modified Hachinski Ischemic Scale (MHIS) score of 4 or less (Rosen 1980).
 13. Female subjects must not be pregnant or breastfeeding. Women of childbearing potential (WOCBP) must have a negative pregnancy test at screening (Visit 1), Visit 3 (prior to study treatment), and Visit 11 (prior to study treatment). WOCBP must agree to use highly effective contraception prior to study entry (Clinical Trial Facilitation Group 2014). A woman is considered of childbearing potential following menarche and until becoming postmenopausal (no menses for at least 2 years without an alternative cause). Should a woman become pregnant or suspect she is pregnant while she or her partner is participating in the study, she should inform her treating physician immediately.

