 16. Current, active liver disease or known hepatic or biliary abnormalities.
 17. Uncontrolled diabetes defined as hemoglobin A1c (HbA1c) > 7.5%.
 18. Clinically significant abnormalities in complete blood count, complete metabolic panel, serum albumin, serum lipids, coagulation, or levels of thiamine, pyridoxine, cobalamin, and thyroid stimulating hormone.
 19. Positive urine drug screen. The presence of opioids, benzodiazepines, and/or amphetamines in the urine drug screen may be allowed if these are prescribed and the dose stable for at least 8 weeks prior to screening.
 20. Hemoglobin < 10 g/dL in women and < 11 g/dL in men.
 21. Urine protein-to-creatinine ratio (UPCR) of > 1.5 grams of protein per gram of creatinine.
 22. Inadequate venous access to allow IV drug delivery or multiple blood draws.
 23. Concurrent participation in any other therapeutic treatment trial. If there was prior clinical trial participation, subject must have discontinued investigational agents for at least 30 days for small molecules, and 1 year for active or passive immunotherapies prior to screening.
 24. If on deep brain stimulation (DBS), DBS surgery within 12 months of screening and/or a change in DBS settings within 12 weeks of screening. DBS settings must not be changed at any point during the subject's participation in the trial.
 25. Presence of a pacemaker or any other implant that would be an MRI contraindication, including DBS if not MRI compatible.
 26. More than 2 lacunar strokes or other clinically-relevant imaging abnormality on screening MRI.
 27. Any other condition and/or situation that the investigator believes may interfere with the safety of the subject, study conduct, or interpretation of study data.

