8.4.3 ADVERSE EVENTS OF SPECIAL INTEREST

Please note that for an event to be classified as an AE of special interest (AESI), the event should meet the definition of an Adverse Event per [Section 8.1.1](#). Thus, if the investigator considers the event to be an AE, and it meets one or more of the criteria listed below, then the event should be classified as an AESI and

reported according to the timeframe specified.

The following will be considered AEs of special interest (AESI) if they qualify as AEs per the preceding paragraph:

- Clinically significant peripheral edema or pulmonary edema.
- Clinically significant systolic BP >160 but <170 mmHg over consecutive timepoints spanning 30 or more minutes.
- Clinically significant systolic BP <90 or >170 mmHg at a single timepoint.
- Clinically significant diastolic BP >100 but <110 mmHg over consecutive timepoints spanning 30 or more minutes.
- Clinically significant diastolic BP <60 or >110 at a single timepoint.
- A change of >25% from baseline in systolic and/or diastolic BP.
- Reduced kidney function (eGFR < 45 mL/min/1.73 m²).
- Suspected transmission of blood-borne infectious agents.

AESI occurring during the study should be reported within 48 hours of observation or learning of the event, unless the event is serious, in which case the event must be reported according to the timeframes specified in [Section 8.4.2.1](#).

Note: Blood pressures meeting the parameters above that are not considered adverse events need not be reported within the 48-hour window. Rather, these will be considered “blood pressures of special interest” and analyzed separately.

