14.3.4 Abnormal Laboratory Value				
NA				

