Subject ID	Treatment [1]	Parameter (unit)	Date of Assessment (Study Day)	Standard Results	Change from Baseline [2]	Reference Range [3]	Reference Range Flag	Accession Number	Comments/Reason Not Done
XXXXXX	XXXXXXXXXX	Red Blood Cell Count	DDMMYYYYY (X)	XX		XX - YY		XXXXXXXXXX	
			DDMMYYYYY (X)	XX	XX	XX - YY		XXXXXXXXXX	
			DDMMYYYYY (X)	XX	XX	XX - YY		XXXXXXXXXX	
			DDMMYYYYY (X)	XX	XX	XX - YY	XXX	XXXXXXXXXX	
			DDMMYYYYY (X)	XX	XX	XX - YY		XXXXXXXXXX	
			DDMMYYYYY (X)	XX	XX	XX - YY		XXXXXXXXXX	
			DDMMYYYYY (X)	XX	XX	XX - YY		XXXXXXXXXX	
			DDMMYYYYY (X)	ND				XXXXXXXXXX	XXXXXXXXXX
			DDMMYYYYY (X)	XX	XX	XX - YY		XXXXXXXXXX	

Abbreviations: A = abnormal; CS = clinically significant; H = high; L = low; ND = not done.

Note: Study day is calculated relative to the date of first dose of study drug.

[1] Treatment is based on treatment received.

[2] Baseline is the Screening Visit 1.

[3] Reference range is used to identify potentially clinically significant laboratory values.

Programming note: update abbreviations to reflect actual data. If test was not done, set results to ND; make sure last column is populated accordingly

Listing 16.2.8.1.2
Clinical Laboratory Data: Serum Chemistry
All Subjects

(Same shell as Listing 16.2.8.1.1)

Listing 16.2.8.1.3
Clinical Laboratory Data: Urinalysis
All Subjects

(Same shell as Listing 16.2.8.1.1; remove "(unit)" from 2nd column header)

Listing 16.2.8.1.4
Clinical Laboratory Data: Urine Drug Screen and Pregnancy Tests
All Subjects

(Same shell as Listing 16.2.8.1.1; remove "(unit)" from 2nd column header; do not display Reference Range or Accession number columns)

Listing 16.2.8.1.5
Clinical Laboratory Data: Coagulation
All Subjects

(Same shell as Listing 16.2.8.1.1)

Listing 16.2.8.1.6
Clinical Laboratory Data: Immunology
All Subjects

(Same shell as Listing 16.2.8.1.1)

Listing 16.2.8.1.7
Clinical Laboratory Data: Serology
All Subjects

(Same shell as Listing 16.2.8.1.1; remove "(unit)" from 2nd column header)

Statistical Analysis Plan,
 Sponsor: Alkermes, Inc.
 Protocol Number ALK6021-201
 PCN Number ALKA7951

Listing 16.2.8.2.1
 Vital Signs
 All Subjects

Subject ID	Treatment [1]	Study Visit	Date of Assessment (Study Day)	Body Temperature (C)	Heart Rate (beats/min)	Respiration Rate (breaths/min)	Height (cm)	Weight (kg)	Abnormal?
XXXXXX	XXXXXX	XXXXXX	DDMMYYYY (X)	XX.X	XX	XX	XX.X	XXX	XXX
		XXXXXX	DDMMYYYY (X)	XX.X	XX	XX		XXX	
		XXXXXX	DDMMYYYY (X)	XX.X	XX	XX		XXX	
		XXXXXX	DDMMYYYY (X)	ND	ND	ND		ND	

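### Measured eGFR below 45 is counted only when the investigator declares an adverse event; no planned table counts it from laboratory data

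*SAP*

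**What the plan says.** Protocol 8.4.3 lists "Reduced kidney function (eGFR < 45 mL/min/1.73 m²" among the AESIs, under a condition stated just above the list: "Thus, if the investigator considers the event to be an AE, and it meets one or more of the criteria listed below". Protocol 7.2.1 leaves the clinical significance of an out-of-range value to the investigator and sends significant values to the adverse-event page of the CRF. SAP 9.1.3 tabulates AESIs from those records, by system organ class, preferred term and arm (Table 14.3.2.3).

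For laboratory data, SAP 9.2 plans:
- observed values and changes from baseline by visit and arm;
- shifts by visit, classed as below, within or above the normal range;
- listings: "Subjects with significant laboratory abnormalities will be identified in data listings".

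SAP 9.2 does not define a significant abnormality. The listing shell uses the laboratory's own range: "Reference range is used to identify potentially clinically significant laboratory values". In SAP 13.3, Table 4, the section headed "14.3.4 Abnormal Laboratory Value" is marked not applicable.

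Blood pressure is handled differently. The note closing Protocol 8.4.3 says that qualifying pressures not judged to be adverse events are analysed separately. SAP 9.3 counts pressures of special interest from the vital-signs source data, by visit, timepoint and arm. Its cut-offs differ from those in 8.4.3, which is a separate matter.

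**The concern.** The renal criterion is numeric, is measured centrally, and sits on the same list as blood pressure, yet it has no count that is independent of the investigator's judgement. A value below 45 that the investigator does not regard as an adverse event enters no table of subjects.

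Inclusion criterion 10 sets the entry floor at the same figure as the AESI limit ("Renal function as defined by estimated glomerular filtration rate (eGFR" at least 45). Any later value below 45 in a correctly enrolled subject is therefore a new crossing. Safety is the primary objective, so readers of the study report will want the number of crossings per arm. They would have to build it by hand from the listings.

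**Working it through.** **1. Is there a count anywhere?** The planned outputs that could carry one are these:
- The AESI table (14.3.2.3) counts declared events only.
- The chemistry summary (14.3.5.2.1) gives n, mean, SD, median, minimum and maximum by visit. A minimum below 45 shows that at least one subject was there, but not how many.
- The chemistry shift table (14.3.5.2.2) gives counts by visit against the normal range.
- The listings give individual values flagged by reference range.
- On-site pre-infusion creatinine is not summarised (SAP 9.2).
- Unscheduled results replace a missing scheduled value if they fall in the visit window (SAP 6.1.5); otherwise they are only listed.

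None gives subjects per arm with any post-baseline eGFR below 45.

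**2. Can the shift table substitute?** Let L be the laboratory's lower limit for eGFR. The documents do not state it, so a range is assumed. A value is Low if it is below L and Normal otherwise.

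| eGFR, baseline to later | Newly below 45? | L = 30 | L = 45 | L = 60 | L = 90 |
|---|---|---|---|---|---|
| 46 to 38 | yes | Normal to Normal | Normal to Low | Low to Low | Low to Low |
| 58 to 44 | yes | Normal to Normal | Normal to Low | Low to Low | Low to Low |
| 75 to 44 | yes | Normal to Normal | Normal to Low | Normal to Low | Low to Low |
| 62 to 58 | no | Normal to Normal | Normal to Normal | Normal to Low | Low to Low |

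With L = 60, the fall from 62 to 58 appears as a shift, while the fall from 46 to 38, which meets the AESI limit, does not. Only L = 45 makes *Low* mean below 45. Even then, the table is split over seven post-baseline visits (6, 8, 9, 14, 16, 17 and 19). One subject can be Low at several of them, so the visit counts cannot be added up to subjects.

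**3. What is at stake for the safety bound?** The plan's own figure (Protocol 10.5, SAP 3.2) is an upper bound of about 5% with 60 active subjects. It reproduces: 3/60 = 5.0%, and the exact one-sided 95% bound is 1 − 0.05^(1/60) = 4.87%.

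Suppose that a share s of falls below 45 is declared as an adverse event. The documents give no s, so a range is assumed. Zero recorded renal AESIs then bounds the laboratory-defined rate at 4.87%/s. If the true rate is 5%, the chance of recording at least one case is 1 − (1 − 0.05s)^60.

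| s | Bound after zero recorded | Chance of at least one recorded |
|---|---|---|
| 1.00 | 4.9% | 95% |
| 0.75 | 6.5% | 90% |
| 0.50 | 9.7% | 78% |
| 0.25 | 19.5% | 53% |

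The s = 1 row is what a direct laboratory count would deliver if all 60 subjects had a post-baseline value.

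**The case against.** The other side has good points, and several limit the finding.

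- **Significant falls are tabulated.** A reader might infer that abnormal values reach only the listings, or that the renal AESI is never counted. The documents do not support either reading. Under Protocol 7.2.1 and 8.1.1, clinically significant values are adverse events, so they enter the TEAE tables and, if below 45, the AESI table. What escapes is a value below 45 judged not to be an adverse event.
- **Extreme falls would be visible.** The by-visit minima, the minima of change from baseline and the planned boxplots would reveal a large drop. They do not count subjects, so the gap remains.
- **The SAP follows the Protocol.** Protocol 10.4.4 itself foresees shifts relative to the reference range. Protocol 2.3.1 names hypotension as an identified risk and names no renal risk, which may explain why blood pressure received more attention. It does not explain why a listed numeric AESI has no count.
- **eGFR is not excluded from analysis.** Note i to SAP Table 1 omits it, but that is a collection schedule. SAP 9.2 summarises each parameter, and Protocol 7.1.1.2.8.3 collects eGFR. This needs a clarification only.
- **Haemoglobin.** It is tempting to extend the point, since entry is barred only at "Hemoglobin < 10 g/dL in women and < 11 g/dL in men". Those are eligibility limits. No on-study haemoglobin limit is stated, so there is no protocol threshold to count against.

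**Conclusion.** The point holds for eGFR. No planned table counts measured values below 45 that are not declared adverse events, and the shift table cannot fill the gap. The missing count follows from the text alone and needs no assumed figure.

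Masking as *Low to Low* is conditional. It requires a laboratory lower limit above 45 and a subject who enters between 45 and that limit. The 6.5% to 19.5% bounds are likewise illustrations over assumed declaration shares, not estimates.

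A reader might also turn an assumed share of low-eGFR entrants into a number of subjects who cross the limit. The documents do not give that share, and the result would be a pool at risk, not a count of crossings.

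A related inconsistency is for the sponsor to reconcile. Protocol Appendix 11, section 3, requires pre-infusion creatinine and haemoglobin to be documented within normal limits, while inclusion criterion 10 and exclusion criterion 20 set entry limits that may lie below normal. This review takes no view on which should prevail.

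**What to change.** In SAP 9.2, add one Safety Set table from central laboratory data. By arm, it should give:
- the number of subjects with any post-baseline eGFR below 45 mL/min/1.73 m², regardless of adverse-event status;
- the denominator, namely subjects with at least one post-baseline value;
- the 95% Wilson interval already used in SAP 9.1;
- a cross-tabulation against reported renal AESIs.

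State that unscheduled central samples are included in this worst-value table as an explicit exception to SAP 6.1.5 and 9.2. Name eGFR among the analysed chemistry parameters, in line with Protocol 7.1.1.2.8.3.

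The cost is some SAP wording and one extra table from data already collected. No visit, sample or clinical rule changes. The downside for the sponsor is that the laboratory count may look less favourable than the AESI count.
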